APPENDIX II: OUTCOMES, DIAGNOSTICS, AND FOLLOW-UP EVALUATIONS

CONDITION	PRODUCT USE	EVALUATION	FOLLOW-UP AND TREATMENT ACTION
Deep Epithelial Disruption (Ulceration) excluding findings observed by colposcopy only	Hold study gel (until evaluated)	Swab for herpes simplex culture. Perform syphilis serology (Herpes serology optional)	Re-evaluate in 48 - 72 hours and reinstate gel use if resolved. If the ulcer has become worse or not healed in 48 - 72 hours, follow the lesion per local standard of care. Ask participant to return in 7-10 days for follow up syphilis serology. If there is reoccurrence and there is no other etiology, then consider permanent discontinuation.
Superficial Epithelial Disruption (Abrasion/Peeling) excluding findings observed by colposcopy only	Continue	Naked eye evaluation with or without colposcopy	Re-evaluate by speculum examination in 48 - 72 hours. If condition is significantly worse, hold study gel. Otherwise continue gel use.
Localized erythema or edema: area of less than 50% of vulvar surface or combined vaginal and cervical surface excluding findings observed by colposcopy only	Continue	Naked eye evaluation with or without colposcopy	If asymptomatic, re-evaluate at next regularly scheduled visit. If symptomatic, re-evaluate by speculum examination in 5 - 7 days. If worsened significantly, hold study gel use, until further evaluation is scheduled. Otherwise, continue gel use.
Generalized erythema or severe edema: area of more than 50% of vulvar surface or combined vaginal and cervical surface affected by erythema excluding findings observed by colposcopy only	Hold study gel (until evaluated)	Naked eye evaluation with or without colposcopy	Re-evaluate in 48 - 72 hours and reinstate gel use if resolved. If there is reoccurrence and there is no other etiology, then consider permanent discontinuation.
Abnormal vaginal discharge	Hold study gel (until evaluated)	Perform wet mount for Candida vaginitis, trichomoniasis, and	Provide treatment and permanently discontinue gel use for all cases of trichomoniasis,

		BV	symptomatic Candida vaginitis, and symptomatic bacterial vaginosis. Gel use may be continued without treatment in the presence of asymptomatic Candida vaginitis and/or asymptomatic bacterial vaginosis.
--	--	----	---

Unexpected genital bleeding	Continue (at clinician's discretion)	Naked eye evaluation with or without colposcopy	If determined to be due to deep epithelial disruption, refer to guidelines in this table. Otherwise continue gel use.
Presumed cervicitis (findings on exam such as mucopurulent cervical discharge)	Hold study gel (until evaluated)	Evaluate for N. gonorrhoeae and C. trachomatis	Provide treatment and permanently discontinue gel use for all cases of cervicitis.
Genital petechia(e) excluding findings observed by colposcopy only	Continue	Naked eye evaluation	No further evaluation or treatment required.
Genital ecchymosis excluding findings observed by colposcopy only	Continue	Naked eye evaluation with or without colposcopy.	No further evaluation or treatment required.
EAE that is judged by the site investigator or designee to be definitely, probably, possibly, or probably not related to the study gel or applicator	For Grades 1, 2, and 3 - Hold study gel (until evaluated) For Grade 4 – Permanent Discontinuation	Evaluate as according to current clinical practice at the site Not applicable	Provide treatment as clinically indicated, when resolved reinstate gel use at clinician's discretion Not applicable

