8.2 Clinical Data Safety Review

A multi-tiered safety review process will be followed for the duration of this study. The study site investigators are the first layer of this tiered system and are responsible for the initial evaluation and reporting of safety information at the participant level, and for alerting the PSRT if unexpected concerns arise. Participant safety is also monitored at the Network level through a series of routine reviews conducted by the SDMC Clinical Affairs staff, the PSRT, and study sponsors. Additional special reviews may also be conducted as dictated by the occurrence of certain events.

All EAE reports submitted to the DAIDS Safety Office will be synchronously sent by the sites to the DAIDS Medical Officer, NICHD Medical Officer, SDMC Clinical Affairs Research Nurse, and the Protocol Chair for review. The SDMC Clinical Affairs staff review AEs, events requiring expedited reporting to DAIDS, and events that meet safety pause criteria.

During the active product use phase of the trial, the PSRT will review clinical and laboratory safety reports (blinded to treatment assignment) and conduct calls every two weeks, or as needed, to review the data as appropriate. The content, format and frequency of these reports will be agreed upon by the PSRT and the SDMC in advance of study implementation. In addition to these routine safety data reviews, the PSRT will convene on an ad hoc basis to make decisions regarding the handling of any significant safety concerns. If necessary, experts external to the MTN representing expertise in the fields of microbicides, biostatistics, and medical ethics may be invited to join the PSRT safety review.

After the product use and the final safety visits are completed, less frequent reporting and safety reviews may be conducted at the discretion of the MTN-004 PSRT.

Decisions regarding permanent discontinuation of study gel in individual participants will be made by the PSRT based on careful review of all relevant data and may involve sponsor consultation with the US Food and Drug Administration (FDA).

Accrual and overall study product use for all participants will be suspended for a data safety review by the PSRT if any two women enrolled in the study experience the same safety or toxicity endpoint, defined as:

1. Having at least one grade 3 or higher adverse experience during follow up judged by the investigator to be definitely, probably, or possibly related to the study gel or applicator, or:

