9.1 Toxicity Management

Based on results from the first Phase 1 study of VivaGel[®], toxicity in study participants is not expected in this trial. In response to AEs reported by study participants and/or observed upon exam by study staff, the study site principal investigator or designee will recommend either continuation or withholding study gel use consistent with the criteria in Appendix II.

Study gel use also will be withheld or discontinued in the event of an Expedited Adverse Event (EAE) that is judged by the site principal investigator or designee to be definitely, probably, possibly, or probably not related to the study gel or applicator. Unless the participant withdraws her consent, she will remain in the study to complete the safety

evaluations (unless clinically contraindicated) according to Appendix I, and/or as specified in Appendix II.

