9.4.1 Criteria for Permanent Study Product Discontinuation for an Individual Participant

The criteria for permanent discontinuation of further study product use for an individual participant are:

- Signs or symptoms of STI(s)/RTI(s) requiring treatment according to the judgment of the investigator
- Study product-related toxicity (see Section 9.1)
- Pregnancy or breastfeeding
- Completion of regimen as defined in the protocol
- Request by participant to terminate treatment
- Clinical reasons determined by the physician

The participant will continue to be followed with the participant's permission if study product is discontinued. No subsequent modifications to the visit schedule and duration of continued follow-up will be made, except no study product will be administered.

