Study Physician: A physician listed on the Form FDA 1572 for IND studies or on the DAIDS Investigator of Record Agreement (IOR) for non-IND studies. (DAIDS)

Suspected Adverse Drug Reaction (SADR): An adverse event that could potentially have a causal relationship to a study agent (definitely, probably, possibly, probably not related or for deaths, pending). (DAIDS)

Toxicity: An adverse event that has an attribution of possibly, probably, or definitely related to a study agent. (DAIDS) NOTE: This term should not be used for expedited reporting of adverse events to DAIDS.

Unexpected Event: An adverse event, the nature or severity (intensity) of which is not consistent with the applicable product information (Investigator's Brochure, package insert, or summary of product characteristics for a US FDA-approved study agent. (DAIDS)

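### After a resolved Grade 3 product-related event the site may restart gel without prior PSRT or Medical Officer agreement, and Section 9.4.1 leaves unclear whether restart is allowed at all

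*Supplement*

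**What the plan says.** Section 9.4.1 gives the criteria for permanently stopping gel in an individual. One is "Study product-related toxicity (see Section 9.1"; it carries no grade.

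Section 9.1 tells the site principal investigator or designee to follow Appendix II when recommending that gel be continued or withheld. It adds: "Study gel use also will be withheld or discontinued in the event of an Expedited Adverse Event (EAE", where the event is judged definitely, probably, possibly or probably not related. It does not say when withholding applies and when discontinuation does.

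The EAE row of Appendix II reads "For Grades 1, 2, and 3 - Hold study gel (until evaluated", then "Provide treatment as clinically indicated, when resolved reinstate gel use", with restart left to the clinician. Within that row only Grade 4 is a permanent stop.

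Section 8.2 states: "Decisions regarding permanent discontinuation of study gel in individual participants will be made by the PSRT". It also provides that "the PSRT will convene on an ad hoc basis to make decisions regarding the handling of any significant safety concerns". Accrual and product use are suspended "if any two women enrolled in the study experience the same safety or toxicity endpoint", the endpoints being Grade 3 or higher and at least possibly related. The visible text of Letter of Amendment #1 leaves these rules unchanged.

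**The concern.** A site with a woman whose definitely related Grade 3 event has resolved finds product-related toxicity listed as a permanent stop in one place and a discretionary restart in another. The three sites could handle the same event differently, and a woman could be re-exposed before anyone outside the site has considered it.

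The participants are healthy volunteers for whom Section 13.3 expects no direct benefit beyond screening and referral. Section 2.18.2 calls this the first study of the gel in sexually active women. The completed studies summarized in Section 2.10 report no related Grade 3 event, so one here would be new information.

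The plan is stricter elsewhere. Appendix II stops gel permanently for cervicitis, trichomoniasis, and symptomatic candidiasis or bacterial vaginosis. Under Section 8.2, if a pause is imposed and lifted, every woman then in active follow-up stops product, including those with no event. The first woman with a severe related event, before any pause, may resume.

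**Working it through.** **1. Does a related Grade 3 event fall in the EAE row?** Yes. Section 8.4.2 adopts the Intensive Level of reporting, and Appendix IV, 3.1.2, adds Grade 3 suspected reactions to that level.

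**2. Stop or restart?** Two readings are open.
- *9.4.1 by itself:* related toxicity of any grade ends product use.
- *Following the references, 9.4.1 to 9.1 to Appendix II:* Grades 1 to 3 are held and may restart; Grade 4 stops.

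No sentence says which governs.

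**3. Must anyone agree before restart?** Each safeguard, checked against the time of restart:
- *EAE report (Appendix IV, 4.0):* due within 3 business days of recognition. The EAE row sets no minimum wait, and the deep-disruption and generalized erythema/severe edema rows allow restart on re-evaluation at 48 to 72 hours if resolved. Restart can precede the report.
- *Medical Officers (8.4.1):* they receive the report and reach a decision, but its subject is not stated and gel is not held for it.
- *PSRT (8.2):* calls are every two weeks or as needed, against 14 days of dosing. It decides permanent discontinuation; restart is not mentioned.
- *Site's duty to alert the PSRT to unexpected concerns (8.2):* no link to restart.
- *Study pause (8.2):* needs a second woman, so it does not govern the first.

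None is a condition of restart, on either reading in step 2.

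**4. How likely is such an event?** The first affected woman meets the gap whether or not a second follows, so the quantity is P(at least one) = 1 − (1 − p)^n. Table 17 of the protocol gives 0.17 at 1% and 0.60 at 5% for n = 18. These reproduce: 1 − 0.99^18 = 0.17 and 1 − 0.95^18 = 0.60. Seven of the 61 women were enrolled under Version 2.0 and are beyond the reach of an amendment, leaving at most 61 − 7 = 54.

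| Women sharing the rate | P(≥1), 1% | P(≥1), 5% | Expected (n × p), 1% | Expected, 5% |
|---|---|---|---|---|
| 18 (VivaGel only) | 0.17 | 0.60 | 0.18 | 0.90 |
| 54 (all Version 3.0) | 1 − 0.99^54 = 0.42 | 1 − 0.95^54 = 0.94 | 0.54 | 2.7 |

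The rates are assumed. Earlier data do not exclude them: no Grade 3 or 4 event in the 35 women given the gel in SPL7013-004 leaves a one-sided 95% upper limit of 1 − 0.05^(1/35) = 8.2%.

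**5. How much re-exposure could follow?** With two doses a day on Days 0 to 13, doses left = 2 × (14 − restart day). For an event found on Day 7, restart on Day 9, 10, 12 or 14 leaves 10, 8, 4 or 0 doses. Resolution times are assumed. The 5-day case (restart on Day 12) borrows the mean duration of the mild Version 2.0 events in Section 2.18.4; a Grade 3 event may last longer.

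**The case against.** The strongest reply is that the sections agree once the pointers are followed: 9.4.1 sends the reader to 9.1, 9.1 to Appendix II, and Appendix II says which events are held and which end product use. A reader might infer an outright contradiction from 9.4.1 read alone, supported by the Appendix IV definition of toxicity: "An adverse event that has an attribution of possibly, probably, or definitely related to a study agent". The documents do not support that. The definition belongs to a general reporting manual, carries its own note against using the term for expedited reporting, and is not adopted by 9.4.1 or 9.1. Read literally, 9.4.1 would also end product use for mild related findings that Appendix II tells sites to continue through. This objection stands and reduces the conflict to an ambiguity.

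A reader might also infer that re-exposure would go unsupervised. It would not: the row requires hold, evaluation, treatment and resolution first, EAE reports go to the Medical Officers and the Protocol Chair, and the PSRT can meet ad hoc. What remains is order in time, since none of the outside review has to precede restart.

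Thirdly, a reader might infer that Grade 3 related events should always end product use. That is a design choice; nothing in the documents shows that restart after full resolution is unacceptable in itself.

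Finally, the study-specific procedures are not shown and may cover hold and resume communication. That is possible, but the protocol's own restart rule does not refer to them.

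**Conclusion.** The point holds in a limited form and is worth fixing. The sections leave the handling of a resolved Grade 3 related event ambiguous. On either reading, the protocol does not require PSRT or Medical Officer agreement before restart, although Section 8.2 makes this grade and relatedness the threshold for pausing the whole study and gives the PSRT individual permanent-discontinuation decisions.

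The chance that the situation arises at all is 0.17 to 0.60 if only 18 VivaGel users are at risk and 0.42 to 0.94 if all 54 share the rate, for assumed rates of 1% to 5%. These are not probabilities of re-exposure. That would need the chance of resolution within dosing and the chance that the clinician restarts, and the documents give neither. The conclusion takes the clinician in the EAE row to be the site clinician, as Section 9.1 suggests.

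**What to change.** 1. In the EAE row of Appendix II, for Grade 3 events judged definitely, probably or possibly related, keep gel on hold until the PSRT has given documented approval to restart. Apply the same condition to Grade 3 related findings in the deep epithelial disruption and generalized erythema/severe edema rows.
2. Reword the toxicity criterion in Section 9.4.1 so that it applies as Appendix II specifies, bringing 9.4.1, 9.1 and Appendix II into agreement. Handling of Grade 1 and 2 findings stays as it is, and permanent discontinuation at Grade 3 need not be mandatory.

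The cost is a letter of amendment with IRB review, and a short delay to restart with possible loss of a few doses for an expected 0.5 to 2.7 women if all 54 share a 1% to 5% rate (0.2 to 0.9 if only 18 VivaGel users are at risk). The PSRT already convenes ad hoc, so no new body is needed. Under Section 9.4.1, a woman whose product is stopped continues in follow-up with her permission.

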APPENDIX III: HIV ANTIBODY TESTING ALGORITHM

Note: HIV positive results will only be reported to participants once the result is confirmed by Western Blot Testing. Once a participant's HIV status is confirmed, sites will follow site specific SOPs for notification to local agencies.

1.0 PURPOSE OF MANUAL

1.1 Purpose

The purpose of this Manual is to describe the criteria and method for expedited reporting of certain serious and other reportable adverse events to the Division of AIDS (DAIDS), National Institute of Allergy and Infectious Diseases (NIAID), through the DAIDS Safety Office.

1.2 Scope

This Manual applies only to those clinical studies/trials requiring expedited reporting of adverse events to the DAIDS Safety Office as stated in the protocol. This Manual applies to all study agents specified in the protocol as requiring expedited reporting to DAIDS. Although not covered under this Manual, note that DAIDS may require MedWatch reporting (using e.g., Form FDA 3500A or CIOMS I Form) to the Food and Drug Administration (FDA) and/or DAIDS for some studies. MedWatch reporting may only be applied to studies/trials of US FDA-approved study agents. Any requirements for MedWatch reporting will be identified in the study/trial protocol.

1.3 Introduction

For adverse events requiring expedited reporting to DAIDS, sites must follow the general reporting requirements and procedures described in this Manual. In order to fully define the expedited adverse event reporting requirements that apply to an individual study/trial, the protocol will specify:

- One of three Levels of Adverse Event Reporting (Section 3.1) and any other adverse events to be reported on an expedited basis (Section 3.2).
- The duration of the protocol-defined expedited reporting period.
- The name or category of each study agent (US FDA-approved or investigational) that requires expedited reporting of adverse events to DAIDS. This may include study agents in addition to those provided by the study/trial.

2.0 DESCRIBING AN ADVERSE EVENT BY SERIOUSNESS, SEVERITY, RELATIONSHIP TO STUDY AGENT, AND EXPECTEDNESS

The criteria for expedited reporting of adverse events to the DAIDS Safety Office include the seriousness of the outcome of the event, the severity (intensity) of the event, its relationship to study agent, and (only for the Targeted Level) expectedness, i.e., whether the adverse event is expected or unexpected.

2.1 Seriousness

The first consideration for expedited reporting of adverse events to DAIDS is the seriousness of the outcome of the event. The April 1996 International Conference on Harmonisation (ICH) guidance, "Good Clinical Practice: Consolidated Guidance," (ICH E6) defined a serious adverse event (SAE) as "any untoward medical occurrence that at any dose:

- Results in death,
- Is life-threatening,
- Requires inpatient hospitalization or prolongation of existing hospitalization,
- Results in persistent or significant disability/incapacity, or
- Is a congenital anomaly/birth defect.”

“Important medical events that may not be immediately life-threatening or result in death or hospitalization but may jeopardize the patient or may require intervention to prevent one of the outcomes listed in the definition above” may also be considered to be serious (October 1994 ICH guidance (E2A), “Clinical Safety Data Management: Definitions and Standards for Expedited Reporting”).

2.2 Severity (Intensity)

The second consideration for expedited reporting of adverse events to DAIDS is the severity (intensity) of the event. In order to maintain consistency among studies/trials and sites, DAIDS has developed a list of common clinical and laboratory adverse events and defined grade 1 – 5 severity parameters to generate the Division of AIDS Tables for Grading Adult and Pediatric Adverse Experiences (also known as “the toxicity tables”). These tables are located on the DAIDS Safety Office website at <http://rcc.tech-resintl.com>. Unless stated otherwise in the protocol, study staff is required to use the Division of AIDS Tables for Grading Adult and Pediatric Adverse Experiences to determine the intensity of adverse events in order to establish consistency in adverse event reporting to DAIDS. Specific protocols may include additional or modified criteria for grading adverse events that are not included in the current versions of the Division of AIDS Tables for Grading Adult and Pediatric Adverse Experiences.

2.3 Seriousness vs. Severity (Intensity) of Adverse Events and Reporting Criteria

For expedited reporting to DAIDS, the term “severity” (or “intensity”) is described as the grade for a specific event, i.e., mild (Grade 1), moderate (Grade 2), severe (Grade 3), or life-threatening (Grade 4). This is *not* the same as “serious,” which is based on subject/event *outcome or action* criteria usually associated with events that pose a threat to a subject’s life or functioning (ICH E2A).

2.4 Relationship to Study Agent

The third consideration for expedited reporting of adverse events to DAIDS is the judgment of causal association (relationship) between an adverse event and the study agent. The protocol must specify by name or category each study agent (either approved or investigational) that requires expedited reporting of adverse events to DAIDS. The study physician makes the site’s final assessment of the causal association based upon the temporal relationship to administration of the study agent(s), the pharmacology of the study agent(s), and his/her clinical

judgment. The terms used in DAIDS studies/trials to assess relationship of an event to study agent are:

- **Definitely Related.** The adverse event and administration of study agent are related in time, and a direct association can be demonstrated.
- **Probably Related.** The adverse event and administration of study agent are reasonably related in time, and the adverse event is more likely explained by study agent than other causes.
- **Possibly Related.** The adverse event and administration of study agent are reasonably related in time, and the adverse event can be explained equally well by causes other than study agent.
- **Probably Not Related.** A potential relationship between study agent and the adverse event could exist (i.e., the possibility cannot be excluded), but the adverse event is most likely explained by causes other than the study agent.
- **Not Related.** The adverse event is clearly explained by another cause not related to the study agent.
- **Pending.** Pending may be used as a temporary relationship assessment only for death and only if data necessary to determine relationship to study agent are being collected. The site is required to submit a final assessment within 3 business days after reporting the death. If no final assessment is made within 3 business days after the date of submission, the event will be assessed as possibly related to study agent. Any additional information received at a later time, including an autopsy report, should be submitted as a Follow-up Report.

A **suspected adverse drug reaction (SADR)** is an adverse event that could potentially have a causal relationship to the study agent (definitely, probably, possibly, probably not related, or for deaths, pending).

